#### 8.2.5. Antibiotic Treatment Information

Monthly rates of days on concomitant antibiotic treatment will be calculated per subject-month. The monthly rate per subject will be the total number of days on antibiotics of the subject divided by the total duration expressed in months (of 30 days) of the observation period of the subject. For the imputation rules of incomplete start/stop dates refer to Section 6.3. Summaries will be as for a continuous variable.

Annual rates of days on concomitant antibiotic treatment will be calculated per subject-year. The annual rate per subject will be the total number of days on antibiotics of the subject divided by the total duration expressed in years (of 365 days) of the observation period of the subject. For the imputation rules of incomplete start/stop dates refer to Section 6.23.

Summaries will be as for a continuous variable and also by categorizing the number of days on antibiotic treatment according to the following categories:

- 0
- >0 to <7
- 7 to <14
- 14 to <21
- 21 to <35
- 35 to <70
- >=70

Summaries will be done for the number of subjects requiring treatment with antibiotics and the number of days on antibiotic treatment.

In addition, the number and percentage of subjects taking concomitant antibiotic medications will be summarized by ATC Levels 2, 3 and 4.

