- A subject diary (paper) will be dispensed. Full instructions on how to complete the paper diary (including information on how to identify and document AEs) will be given. Subject diaries will include a record of the following: occurrence of AEs (including infections), concomitant medication use (including antibiotic treatment), days lost from school/work due to infections and their treatment, any hospitalization, and the number of days in hospital.
- Health-related quality-of-life assessment will be performed. •
- BT595 will be infused intravenously. •
- Concomitant medications (including prohibited treatments) will be recorded. The type of concomitant medication, dose/schedule, duration, and the indication the concomitant medication was given for will be documented.
- Adverse events will be recorded. •

Treatment Period Visits (Visit 3 through Visit 19, Week 3 through Week 51 [3-Week Schedule] or Visit 3 through Visit 15, Week 4 through Week 52 [4-Week Schedule])

Subjects will attend the study site for a further 17 visits (3-week schedule) or 13 visits (4-week schedule). All assessments will be carried out before BT595 infusion, unless indicated. The following procedures will be performed at each study site visit:

- A physical examination will be performed. •
- Vital signs (pulse, blood pressure, respiratory rate) will be recorded within 30 minutes before each infusion, 15-30 minutes after the start of each infusion, 15-30 minutes after the end of each infusion, and 15-30 minutes after the start of any change in the infusion rate. In any case where the change in infusion rate is sooner than a 15 minute interval, vital signs should be measured prior to the change.
- The vital sign, temperature, will be recorded within 30 minutes before each • infusion only.
- Body weight will be recorded (to calculate subject dose).
- A urine pregnancy test (dipstick) will be performed for all female subjects of • child-bearing potential (≥12 years of age or presence of menstruation at screening).
- Samples for routine safety laboratory parameters (hematology, coagulation, • clinical chemistry, urinalysis) will be taken.
- Samples for IgG trough levels (total IgG) will be taken. The subject's total IgG • trough level result from the previous infusion will be made available before the infusion of BT595 to allow dose adjustment if a subject's trough level was below 5 g/L.
- A subject diary (paper) will be collected and reviewed. ٠

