9.1.1.2 Secondary Efficacy

Secondary efficacy will be determined using the following:

- Immunoglobulin G trough levels (total IgG) before each infusion
- Infections (serious and nonserious, time to resolution of infections, antibiotic treatment for infections, and days lost from school/work due to infections and their treatment)
- Hospitalization
- Fever episodes
- Health-related quality-of-life

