#### Definition of Baseline

Baseline will be defined as the last available value before the first infusion of study medication and may be any visit between screening and day 1 (including the baseline visit [V2]) and unscheduled visit.

Duration of concomitant antibiotic treatment

If medication starts before date of first infusion (Visit 2, Day 1): Duration of concomitant antibiotic treatment [days] = Date of stop of antibiotic treatment – Date of first infusion +1.

If medication starts at/after date of first infusion (Visit 2, Day 1):

Duration of concomitant antibiotic treatment [days] = Date of stop of antibiotic treatment – Date of start of antibiotic treatment + 1

Duration of infusional AE

Duration of AE [hours] = (Date/time of stop of AE – Date/time of start of AE)

Duration of noninfusional AE

Duration of AE [days] = Date of stop of AE – Date of start of AE + 1

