#### 7.5.2. Concomitant Medication

Medications taken at/after first infusion will be summarized as 'Concomitant' medications. Premedications taken to avoid AEs will be classified as concomitant medication, even if administered prior to the first BT595 infusion. Separate outputs will be generated for other concomitant medication, premedication, prohibited medication or treatment and rescue medication (added or changed concomitant medication due to the worsening of underlying disease). If subject has taken a concomitant medication more than once, the subject will be counted only once in the respective total (overall).

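### The antibiotic-days endpoint has no split by indication and no rule for overlapping courses, so prophylaxis can inflate a mean meant to reflect infection burden

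*SAP*

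**What the plan says.** **The endpoint.** SAP 4.2 lists antibiotic treatment among the secondary efficacy endpoints. SAP 8.2.5 gives the rate: "The monthly rate per subject will be the total number of days on antibiotics of the subject". That total is set against the subject's own observation time, counted in 30-day months. A parallel annual rate uses years of 365 days. Neither refers to the reason for the antibiotic.

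**Which antibiotics count.** Timing alone decides what is concomitant (SAP 7.5.2): "Medications taken at/after first infusion will be summarized as 'Concomitant' medications". For courses already running at entry, SAP 6.2 says: "If medication starts before date of first infusion (Visit 2, Day 1): Duration of concomitant antibiotic treatment [days] = Date of stop of antibiotic treatment". From that stop date the rule subtracts the day of the first infusion and adds 1. Days before the first infusion are therefore not counted, but the course is.

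**What the protocol says.** The parameter list in protocol 9.1.1.2 places this item within infections: "antibiotic treatment for infections, and days lost from school/work due to infections". The endpoint list in 9.1.3.2 gives only days of antibiotic treatment per month, and the analysis text in 10.6 uses all days on antibiotics.

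**Whether prophylaxis can occur.** Exclusion criterion (i) in protocol 4.3 concerns an active infection under antibiotic therapy for that infection. Protocol 6.9.2 allows concomitant medication other than immunoglobulins as needed. Nothing bars prophylaxis.

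**What is collected.** Protocol 7.1 requires that "the indication the concomitant medication was given for will be documented".

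**The concern.** The endpoint sits beside infection rates, days lost to infection and hospitalization as a measure of how well BT595 controls infection. A day of long-standing prophylaxis and a day of treatment for a new infection mean different things, yet the planned rate adds them together. Because treatment of an active infection at entry is an exclusion, courses carried across the first infusion are likely to be mostly prophylactic or long-term. That is an inference; the documents do not state it.

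The plan draws this kind of line elsewhere. Hospitalization is reported both overall and due to infection (SAP 8.2.7). Days off school or work are limited to infections and their treatment (SAP 8.2.6). Infusion premedication is identified by a prophylaxis indication (SAP 7.5). Antibiotic days have no such split.

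The trial has no control arm, and SAP 2.2 says efficacy results will be compared with historical and literature data. A mean with an unknown share of prophylaxis is hard to compare with anything.

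A second gap is that SAP 6.2 defines duration for a medication, while SAP 8.2.5 speaks of the subject's days, and no rule connects the two when courses overlap.

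**Working it through.** The documents state no numerical figure for this endpoint, so there is nothing to reproduce. The question is how sensitive the planned mean is to prophylaxis.

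**Inputs from the documents:** N = about 70 enrolled (treated) and at least 50 evaluable (SAP 3.5); a year of 365 days and a month of 30 days (SAP 8.2.5).

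**Assumptions, not in the documents:** k continuous prophylaxis users, from 1 to 5; t therapeutic days per year in each other subject, set at 5, 10 or 20; a full year observed for everyone.

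**Contribution of the users to the mean:** k × 365/N.
- k = 1: 365/70 = 5.2 days/year.
- k = 5: 5 × 365/70 = 26 days/year.

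These are gross contributions. Net of the t days such a subject would otherwise have had, one user shifts the mean by (365 − t)/70, which is 5.1 days/year at t = 5 or 10 and 4.9 at t = 20.

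**Mean and share of all days:** mean = [365k + (N − k)t]/N; share = 365k/[365k + (N − k)t]. For k = 3 and N = 70, 365k = 1095:

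| t (days/year) | Mean with 3 users (days/year) | Share from the 3 users |
|---|---|---|
| 5 | (1095 + 335)/70 = 20.4 | 1095/1430 = 77% |
| 10 | (1095 + 670)/70 = 25.2 | 1095/1765 = 62% |
| 20 | (1095 + 1340)/70 = 34.8 | 1095/2435 = 45% |

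With prophylaxis reported separately, the therapeutic mean in the other subjects stays at t. With N = 50 and k = 3 the shares are 82%, 70% and 54%.

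**Users needed to supply half of all days:** k = Nt/(365 + t). For N = 70 this is 1.0, 1.9 and 3.6 at t = 5, 10 and 20.

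**Median.** Moving 3 of 70 subjects to the top of the distribution shifts the median by at most three places in the ordering. Those subjects would fall in the top category of SAP 8.2.5 (70 days or more), together with any subject treated heavily for infections.

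**Overlap.** Under one reading, record durations are summed; under the other, distinct calendar days are counted.
- Two drugs given together for 10 days: 20 against 10.
- Continuous prophylaxis plus 20 treatment days: 365 + 20 = 385 against 365, or 385/(365/30) = 31.6 against 30 days per 30-day month.
- Two continuous agents: 730/(365/30) = 60 against 30 days per month.

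The SAP does not choose between these readings.

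**The case against.** The strongest reply is that the SAP follows the protocol's operative text. A reader who sees only protocol 9.1.1.2 might infer that the SAP silently removed a restriction to infections. The documents do not support that: protocol 9.1.3.2 and 10.6 already lack it, so SAP 13.1.6 had no change of indication to log. The inconsistency is within the protocol, and the SAP inherits it.

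A reader might also infer that overlapping antibiotics are counted twice. No text says that durations are summed across medications, and the subject-level wording of SAP 8.2.5 can as easily mean calendar days. What is missing is a rule.

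Nor do the documents show that prophylaxis will dominate the result. They give neither the number of users nor the therapeutic days in the others. It is also too strong to say that prophylaxis carries no information on infection burden, since prophylaxis begun during the study could be a response to infections.

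The planned output softens the effect. SAP 6.1 adds the median, minimum and maximum, and SAP 8.2.5 adds day categories and ATC tables. SAP 8.2.2 to 8.2.4 measure infections directly. The endpoint is descriptive, with no test or threshold attached.

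All of this stands, and it limits the weight of the point. It does not supply the missing split: the median is also a pooled statistic, and neither the top day category nor the ATC tables separate prophylaxis from heavy treatment.

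**Conclusion.** As written, the plan yields a pooled antibiotic rate that does not isolate infection-related use, although one section of the protocol frames the parameter that way and the data needed to separate it are recorded. The effect falls on the mean. It is about 5 days/year per continuous user among 70 subjects, or about 5 to 26 days/year for 1 to 5 users. Three users would supply about 77% to 45% of all days if the others average 5 to 20 therapeutic days/year. These sizes rest on assumed numbers of users, assumed therapeutic days and full-year observation; with no continuous users the inflation from that source is nil. The missing overlap rule is a separate, smaller ambiguity. The primary endpoint and its conclusion are not affected. This is a low-cost improvement to a descriptive secondary endpoint and does not threaten the trial's main claim.

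**What to change.** In SAP 8.2.5, classify each concomitant antibiotic course as therapeutic or prophylactic from its recorded indication. Report three lines:

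1. therapeutic antibiotic days, as the infection-related endpoint;
2. prophylactic antibiotic days;
3. the total, which keeps the quantity prespecified in protocol 10.6.

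State that each calendar day with at least one antibiotic counts once per subject, within each line and in the total. Record the split and the counting rule in SAP Section 13, noting that protocol 9.1.1.2 differs from 9.1.3.2 and 10.6 on indication.

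The cost is SAP wording, a review of indications before database lock and one extra split in the tables. No new data are needed.

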### 8.2.6. Rate of Time Lost from School/Work due to Infections and their Treatment

Monthly rates of the number of days subjects are not able to attend school/work due to infections and their treatment will be calculated per subject-month. The monthly rate per subject will be the total number of days off school/work due to infections and their treatment of the subject divided by the total duration expressed in months (of 30 days) of the observation period of the subject. Summaries will be as for a continuous variable.

Annual rates of the number of days subjects are not able to attend school/work due to infections and their treatment will be calculated per subject-year. The annual rate per subject will be the total number of days off school/work due to infections and their treatment of the subject divided by the total duration expressed in years (a) of 365 school/work days and b) of 220 school/working days) of the observation period of the subject.

Summaries will be as for a continuous variable and also by categorizing the number of days lost from school/work according to the following categories:

- 0
- >0 to <7
- 7 to <14
- 14 to <21
- 21 to <35
- 35 to <70
- >=70

Summaries will be done for the number of subjects, total number of subject days during study, and the number of days losing school/work due to infections.

#### 8.2.7. Hospitalization / Hospitalization due to Infection

Monthly rates of the number of days of hospitalization (any hospitalization/ hospitalization due to infection) will be calculated per subject-month. The monthly rate will be the total number of days in hospital of the subject divided by the total duration expressed in months (of 30 days) of the observation period of the subject. Summaries will be as for a continuous variable.

Annual rates of the number of days of hospitalization (any hospitalization/ hospitalization due to infection) will be calculated per subject-year. The annual rate will be the total number of days in hospital of the subject divided by the total duration expressed in years (of 365 days) of the observation period of the subject.

Summaries will be as for a continuous variable and also by categorizing the number of days of hospitalization according to the following categories:

- 0
- >0 to <7
- 7 to <14
- 14 to <21
- 21 to <35
- 35 to <70
- >=70

Summaries will be done for number of subjects (%) with hospitalization and the number of days of hospitalization.

Separate calculation will be generated for hospitalization due to serious bacterial infections (SBI).

#### 8.2.8. Fever Episodes

Fever is defined as a body temperature  $\geq 38^{\circ}$ C ( $\geq 100.4^{\circ}$ F). Fever, which recurs after  $\geq 3$  days without fever will be counted as a new fever episode. The number of days of fever for a given fever episode is defined as the number of days from the first day of a body temperature  $\geq 38^{\circ}$ C ( $\geq 100.4^{\circ}$ F) to the last day with a body temperature  $\geq 38^{\circ}$ C ( $\geq 100.4^{\circ}$ F) to the last day with a body temperature  $\geq 38^{\circ}$ C ( $\geq 100.4^{\circ}$ F) including gaps between days with fever <3 days.

The number of days with episodes of fever will be calculated as the mean number of fever episodes per subject-year as described in Section 8.1.1. The annual rate per subject will be the total number of days with episodes of fever of the subject divided by the total duration expressed in years of the observation period of the subject.

Summaries will be as for a continuous variable and also by categorizing the data according to the categories:

- 0
- 1 to <=2
- 3 to <5
- 5 to <8
- 8 to <10
- 10 to <14
- ≥14

Summaries will be done for number (%) of subjects with fever episodes and total number of days with episodes of fever.

#### 8.3. EXPLORATORY EFFICACY ENDPOINTS AND ANALYSES

#### 8.3.1. The Peds QL™ Questionnaire

Scoring and handling of missing values will be done as recommended in the user manual. Three scores will be calculated: the Total Scale Score (all 23 items), the Physical Health Summary (8 items), and the Psychosocial Health Summary (15 items). The parent proxy-report for children aged 2-4 years consists of 21 items. See Appendix 2 for calculation of scores. The descriptive summary statistics for the total score and the single dimension scores will be provided by visit. In addition, changes from the baseline (Week 0) assessment to the post treatment assessment will be determined. The Peds QL will be presented for each age category separately. The questionnaire was designed for: aged 2 through 4 years, 5 through 7 years, 8 through 12 years, and 13 through 18 years. Both child self-reports and parent proxy-reports will be presented, if applicable.

#### 8.3.2. The EQ-5D™ Questionnaire

Scoring and handling of missing values will be done as recommended in the user manual. Descriptive summary statistics for the single dimension scores "Mobility", "Self-Care", "Usual Activities", "Pain/Discomfort" and "Anxiety/Depression" will be provided by visit. The VAS question 'Your own health state today' will be analyzed by means of descriptive statistics. In addition, changes from VAS baseline (Week 0) assessments to each posttreatment assessment will be determined. The EQ-5D will be presented for each age category separately. The questionnaire was designed for: children 4 to <18 years and adults  $\geq$  18 years. Both child self-reports and parent proxy-reports will be presented, if applicable.

### 9. ANALYSIS OF PHARMACOKINETICS

The summary statistics will be based on according analysis sets and will be done by treatment schedule (3- or 4- week) and overall, if not stated otherwise.

In addition, all PK parameters will be summarized descriptively stratified by age categories, gender, race and region as defined in Section 6.6. Age classes will be presented separately by FDA and by EMA criteria. The pediatric population (young children, children and adolescents) will be presented as a subtotal.

#### 9.1. MEASUREMENTS

Pharmacokinetic endpoints can be found in Section 4.4 of this SAP.

Serum concentrations will be determined for different types of IgG: total IgG, subclass of IgG, and IgG directed against specific antigens, namely, pneumococcal capsular polysaccharide, hemophilus influenzae type B, measles, tetanus toxoid, anticytomegalovirus, and hepatitis B antigens.

PK results of this study will be compared to relevant historical data from previous PID studies with Intratect® (already marketed 10% IVIg from Biotest) and to available data from Bivigam® (a 10% IVIg, which was formerly developed by Biotest)), as well as to available data from the literature.

#### 9.2. HANDLING OF DROPOUTS, MISSING DATA OR DATA BELOW THE LOWER LIMIT OF QUANTIFICATION, OUTLIERS

If the actual time of sampling is missing, the planned time may be used after visual check of the data and adequacy with the rest of the concentration-time profile.

Missing concentration data for all subjects who are administered with scheduled study treatments will be considered as non-informative missing and will not be imputed. No concentration estimates will be provided for missing sample values.

The "PK concentrations" of samples taken outside the permitted time window will be listed and presented graphically on the individual plots using actual time. These data will be also used for PK parameters derivation using actual time. However, concentrations from samples taken outside the permitted sampling windows (mostly trough levels) may be excluded from summary statistics; this will be determined during DRM.

All below limit of quantification (BLQ) values for the serum concentration will be listed in concentration listings and will be set to missing for PK parameters derivation; % of BLQ values will be summarized for each time point within each age category/dosing interval combination.

For the individual PK profiles of serum concentration and for summary statistics of PK concentrations including generation of mean concentration versus time plots the following rules will apply: first BLQ value after quantifiable concentration as well as BLQ values

flanked by two quantifiable concentrations will be set to LLOQ/2, further values below BLQ will be set to zero unless deemed as outliers.

Obvious outliers will be considered as missing data. The outliers may be defined based on data review and comparison with typical values such as unexpected occurrence of BLQ results at the end of infusion, or significantly higher result than the typical max range of concentrations, etc. Data will be listed, but not included in summary statistics.

# 9.3. SAMPLING SCHEDULE FOR TROUGH LEVELS AND DENSE PHARMACOKINETICS

Venous blood samples with corresponding times for each analyte are shown in Table 1 below.

1004675

Table 1. Schedule of IgG type analysis by dosing schedule, age category, type of PK analysis, and time points

Version Final 2.0

Dosing	Age	PK	Time point (week)	Total	lgG	Specific
Schedule	(years)	Set		lgG 	subclasses 	lgG 
Q3W	2 to <6	PK Trough	Baseline	+	-	-
			Post-1 st EOI 	+	-	-
			Predose for all infusions (total IgG)	+	-	-
		Dense PK	Infusion 7 (week 18):			
			optional, sparse sampling at flexible time points 	+	-	-
	6 to <12	PK Trough	Baseline	+	+	-
			Post-1 st EOI 	+	-	-
			Predose for all infusions (total IgG)	+	-	-
			Only baseline and predose (before 7 th infusion)	-	+	-
		Dense PK	Infusion 7 (week 18):			
			Predose, EOI  , 4h, 24h, 4d, 7d, 14d, 21d	+	+	-
	12 to <76	PK Trough	Baseline	+	+	+
		_	Post-1 st EOI 	+	-	-
			Predose for all infusions (total IgG),	+	-	-
			Only baseline and predose (before 7 th infusion)	-	+	-
		Specific Trough PK	Only baseline and predose (before 7 th infusion)	-	-	+
		Dense PK	Infusion 7 (week 18):			
			Predose, EOI  , 4h, 24h, 4d, 7d, 14d, 21d	+	+	+
Q4W	2 to <6	PK Trough	Baseline	+	-	-
			Post-1 st EOI 	+	-	-
			Predose for all infusions for total IgG	+	-	-
		Dense PK	Infusion 5 (week 16):			
			optional, sparse sampling at flexible time	+	-	-
			points 			
	6 to <12	PK Trough	Baseline	+	+	-
			Post-1 st EOI 	+	-	-
			Predose for all infusions (total IgG)	+	-	-
			Only baseline and predose (before 5 th infusion)	-	+	-

Dosing Schedule	Age (years)	PK Set	Time point (week)	Total IgG 	lgG subclasses 	Specific IgG 
		Dense PK	Infusion 5 (week 16): Predose, post-EOI4  4h, 24h, 4d, 7d, 14d, 21d, 28d	+	+	-
	12 to <76	PK Trough	Baseline	+	+	+
		, , , , , , , , , , , , , , , , , , ,	Post-1 st EOI4	+	-	-
			Predose for all infusions (total IgG)	+	-	-
			Only baseline and predose (before 5 th infusion)	-	+	-
		Specific Trough PK	Only baseline and predose (before 5 th infusion)	-	-	+
		Dense PK	Infusion 5 (week 16): Predose, EOI4  4h, 24h, 4d, 7d, 14d, 21d, 28d	+	+	+

EOI – end of infusion

Q3W – dosing schedule for dose administration once per 3 weeks

Q4W - dosing schedule for dose administration once per 4 weeks

<sup>1 Total IgGs will be measured as trough concentrations prior each infusion in local laboratory, and in central lab for samples collected for the dense PK sampling

<sup>2 Subclasses of IgGs will be measured as trough concentrations at baseline and prior to 7th/5th infusion for 3 or 4 –week schedule respectively in local laboratory, and in central lab for samples collected for the dense PK sampling.

<sup>3 Anti-pneumococcal capsular polysaccharide, anti-hemophilus influenzae type B, anti-measles, anti-tetanus, anti-cytomegalovirus, and anti-HBs/hepatitis B concentrations will be measured at central lab (Biotest). This analysis is planned only for subjects 12 years and older.

<sup>4 Pre-dose samples collected within 10-30 min before the start of infusion. Post-infusion (EOI) samples collected within 10-30 min window from the end of infusion, PK sampling windows for 4 and 24 hrs post-infusion -  $\pm 1$  h; for 7, 14, 21 and 28 days -  $\pm 1$  d

<sup>5 For pediatric subjects (2 to <6 years), sparse sampling for PK analysis of total IgG only may be performed at flexible time points within specified time windows after the end of the infusion (note: these samples are optional)

